Hence, we propose to evaluate the overall hypothesis that intestinal chemosensitivity related to increased epithelial permeability and GLP-1 explains symptom severity in patients with functional dyspepsia and in patients with DM and dyspepsia. 24 healthy subjects, 40 patients with DM and GI symptoms, and 40 patients with functional dyspepsia will undergo assessment of intestinal chemosensitivity during duodenal nutrient perfusion, gastric emptying (by scintigraphy), cardiovascular and GI vagal functions (plasma pancreatic polypeptide response to sham feeding and a comprehensive autonomic reflex screen), in vivo assessment of small intestinal permeability (urinary lactulose:mannitol ratio), and upper endoscopy with assessment of epithelial tight junction proteins and permeability on small bowel biopsies. During the nutrient infusion, subjects in each group (ie, healthy subjects, functional dyspepsia and DM) will be randomized to lipid infusion and placebo or lipid infusion {66.7 mL Microlipid (0.5 gm/mL diluted in water to 222 mL)} and exendin 9-39 in the ratio of 1:1. Hormonal responses (i.e., GLP-1, CCK, GIP, glucagon, PYY, C-peptide, and insulin) and plasma glucose will also be evaluated during enteral nutrient infusion. GI symptoms during each perturbation (meal, nutrient infusion) will be evaluated by validated questionnaires. Blood will be collected for DNA-based genetic analyses, initially to assess the relationship of GI sensorimotor dysfunctions and symptoms with SNPs affecting CCK and GLP-1 receptors. The analysis will assess for disturbances in these parameters in functional and DM dyspepsia, investigate associations between symptoms during enteral infusion and hormonal-epithelial functions, and evaluate relationships between daily symptoms and results of testing.

Table of Contents

ABSTRACT.....	1
1 SPECIFIC AIMS	3
2 BACKGROUND AND SIGNIFICANCE.....	5
3 RESEARCH DESIGN AND METHODS.....	7
3.1 Study Design.....	7
3.2 Study Subjects.....	7
3.3 Details of Study Assessments	8
3.4 Gene and Epigenetic Studies	15
3.5 Data Analysis	16
3.6 Potential Pitfalls.....	17
4 HUMAN SUBJECTS	17
5 SAFETY AND ADVERSE EVENTS	19
5.1 Definitions.....	19
5.2 Recording of Adverse Events	21
5.3 Reporting of Serious Adverse Events and Unanticipated Problems.....	22
5.3.1 Sponsor-Investigator reporting: notifying the Mayo IRB.....	22
5.3.2 Sponsor-Investigator reporting: Notifying the FDA.....	22
5.4 Stopping Rules	23
5.5. Medical Monitoring	23
APPENDIX.....	23

1 SPECIFIC AIMS

Upper gastrointestinal symptoms (early satiety, pain, nausea, and vomiting) are not uncommon in diabetes mellitus (DM)¹. These symptoms are often attributed to delayed gastric emptying or gastroparesis. Over a 10-year time period, the risk of developing gastroparesis was 5% in type 1 DM (HR 33, 95% CI 4.0, 274 adjusted for age and gender versus controls), 1% in type 2 DM (HR 7.5 (95% CI: 0.8, 68) adjusted for age and gender versus controls and 1% in controls². However, similar to functional dyspepsia³, the precise contribution of abnormal gastric emptying to symptoms in patients with DM gastroparesis is unclear. Indeed, a majority of patients with DM and delayed gastric emptying are asymptomatic. In our cohort of DM patients with GI symptoms who underwent scintigraphy, a substantial proportion, i.e., 55 of 129 patients (42%) had normal gastric emptying; the remainder had had delayed (36%) or rapid GE (22%)⁴. Moreover, symptoms did not predict abnormal (i.e., delayed or rapid) gastric emptying. Other, small, studies reported impaired gastric accommodation and increased gastric sensation in DM^{5,6} but did not describe the relationship of these abnormalities to upper GI symptoms.

Nutrients and enteral hormones (e.g., CCK, GLP-1) released in response to nutrients also stimulate small intestinal mechano and chemoreceptors or tastant receptors, which are located on or activate vagal afferents. Few studies have explored the contribution of duodenal sensitivity to symptoms in functional dyspepsia. Duodenal acidification induces proximal gastric relaxation, increases sensitivity to gastric distension, and inhibits gastric accommodation to a meal⁷. Duodenal lipid infusion increased the sensitivity to gastric distension in functional dyspepsia⁸⁻¹¹. This sensitizing effect was blocked by a lipase inhibitor or a CCK-A receptor antagonist^{12,13}. We recently observed increased sensitivity to duodenal nutrient (carbohydrate and lipid perfusion) in approximately 50% of patients with functional dyspepsia during lipid and separately carbohydrate infusion, without gastric distention (unpublished observations). Moreover, increased sensitivity was associated with higher plasma concentrations of CCK during lipid infusion and more severe dyspeptic symptoms during daily life. However, the contribution of intestinal chemosensitivity to symptoms in DM is unknown. We recently observed that patients with functional dyspepsia reported more severe symptoms during enteral lipid and carbohydrate infusion. Second, this increased sensitivity was associated with higher plasma concentrations of enteral hormones (e.g., GLP-1 during lipid and carbohydrate infusion), more severe dyspeptic symptoms, and a greater impact on quality of life.

Vagal dysfunction has been implicated as a mechanism for GI sensorimotor dysfunctions in DM¹⁴. The plasma pancreatic polypeptide (PP) response to sham feeding evaluates GI vagal function¹⁵. In clinical practice, assessment of cardiovascular vagal functions is used as a surrogate measure of GI vagal dysfunction. Only 1 study evaluated the relationship between cardiovascular and GI vagal dysfunction (i.e., gastric acid secretion, PP response to sham feeding) and observed a modest correlation¹⁵. The utility of the sham feeding response and cardiovascular measures to predict upper GI sensorimotor dysfunctions has not been evaluated.

A recent study suggests that patients with functional dyspepsia have low-grade mucosal inflammation, abnormalities of cell-to-cell adhesion proteins which predispose to increased epithelial permeability, and a leaky epithelial barrier¹⁶. Type 1 DM is associated with increased small intestinal permeability even in subjects who do not have celiac disease^{17,18}. Moreover, a comparison of 339 type 1 DM patients and 89 first degree relatives observed higher serum zonulin levels in type 1 DM patients than controls or relatives; patients with increased zonulin had increased epithelial permeability¹⁹. The only study which evaluated small intestinal permeability in type 2 DM used suboptimal techniques and reported normal permeability²⁰.

Our *overall hypothesis* is that intestinal chemosensitivity related to increased epithelial permeability and CCK explains symptom severity in patients with DM with upper GI symptoms.

The **specific aims** of this study are to address the following hypotheses in 24 healthy subjects, 40 patients with DM and GI symptoms, and 40 patients with functional dyspepsia:

- 1) **A) Patients with DM and GI symptoms have increased intestinal chemosensitivity compared to controls and B) Intestinal chemosensitivity predicts severity of ongoing upper gastrointestinal symptoms independent of gastric emptying.** Intestinal chemosensitivity will be recorded by evaluating symptoms during duodenal lipid infusion (222 kcal, 222 ml) and placebo or the GLP-1 receptor antagonist exendin 9-39 over 2 hours; plasma hormones (i.e., glucose, CCK, GLP-1, PYY, C-peptide, will also be measured. Delivering nutrients into the duodenum will ensure that hormonal responses are not affected by gastric emptying disturbances. Day-to-day symptoms will be evaluated by the Nepean dyspepsia severity index and the GCSI. The relationship between daily symptoms and intestinal chemosensitivity will be assessed in a model which also incorporates gastric emptying and accommodation.
- 2) **Intestinal chemosensitivity will be A) associated with higher plasma CCK and GLP-1 concentrations B) reduced by the GLP-1 antagonist exendin 9-39 and C) inversely associated with impaired abdominal vagal function.** This hypothesis will be evaluated by comparing intestinal chemosensitivity (a) with plasma CCK and GLP-1 concentrations (b) with and without exendin 9-39 and (c) in patients with and without and GI vagal dysfunction as assessed by the plasma pancreatic polypeptide response to sham feeding.
- 3) **A) Patients with DM and GI symptoms have abnormal epithelial tight junction proteins which predispose to increased epithelial permeability and increased small bowel permeability and B) These structural and functional markers of epithelial permeability are associated with intestinal chemosensitivity.** Intestinal permeability will be measured in vivo by two sugar urine excretion after oral ingestion. Biopsies from the distal second or third portion of the duodenum will be obtained endoscopically, to measure various markers of epithelial structure and function.

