Vagal dysfunction has been implicated as a mechanism for GI sensorimotor dysfunctions in DM¹⁴. The plasma pancreatic polypeptide (PP) response to sham feeding evaluates GI vagal function¹⁵. In clinical practice, assessment of cardiovascular vagal functions is used as a surrogate measure of GI vagal dysfunction. Only 1 study evaluated the relationship between cardiovascular and GI vagal dysfunction (i.e., gastric acid secretion, PP response to sham feeding) and observed a modest correlation¹⁵. The utility of the sham feeding response and cardiovascular measures to predict upper GI sensorimotor dysfunctions is unknown and will be evaluated in this study.

Small intestinal epithelial permeability and mucosal inflammation

A recent study suggests that patients with functional dyspepsia have low-grade mucosal inflammation, abnormalities of cell-to-cell adhesion proteins which predispose to increased epithelial permeability, and a leaky epithelial barrier¹⁶. Type 1 DM is associated with increased small intestinal permeability even in subjects who do not have celiac disease^{17,18}. Moreover, a comparison of 339 type 1 DM patients and 89 first degree relatives observed higher serum zonulin levels in type 1 DM patients than controls or relatives; patients with increased zonulin had increased epithelial permeability¹⁹. The only study which evaluated small intestinal permeability in type 2 DM used suboptimal techniques and reported normal permeability²⁰. However, a high fat diet induced glucose intolerance, decreased intestinal tight junction proteins, increased epithelial permeability, and plasma concentrations of circulating cytokines in OLETF mice, which is a

Small intestinal dysmotility, more frequently characterized by reduced than by increased motility²⁷, may also contribute to gastric stasis in DM. We recently observed increased sensitivity during duodenal carbohydrate and separately lipid perfusion in approximately 50% of patients with functional dyspepsia (Figure 1). Moreover, increased sensitivity was associated with higher plasma concentrations of GLP-1 during lipid infusion and more severe dyspeptic symptoms during daily life (unpublished data). Previous

spontaneous CCK-1 receptor knockout mouse and an animal model of obesity³². Given the similarities between this mouse model and type 2-DM in humans, it is conceivable that epithelial permeability is also increased in type 2 DM.

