3.5 Data Analysis

Chemosensitivity will be measured using a 100mmVAS anchored at each end (left end:No symptoms, right end: Severe symptoms). The distribution of this measure will be checked for its approximation to a gaussian distribution. An analysis to provide preliminary data for a new grant submission will be examined after approximately 15 subjects (5 DM, 10 controls) have completed the studies, but there is no intention of stopping the study based on the preliminary results. We anticipate conducting this analysis in July 2014 or thereafter.

Question	Summary Parameter	Statistical analysis
Sensation (symptoms) during enteral infusion (Aim 1)	VAS score	i) compare VAS scores in response to lipid infusion + exendin vs. lipid infusion + placebo separately for each group using a 2-sample t-test or Wilcoxon rank sum test ii) compare the delta VAS scores (exendin – placebo) to assess the association with subject status (FD,DM, and controls) using an ANOVA model (adjusting for covariates, eg, type of DM) or Kruskal-Wallis test.
Relationship between intestinal chemosensitivity and severity of ongoing upper GI symptoms	Mean symptom score and QoL defined by the Nepean dyspepsia index and GCSI diary	Multiple linear regression with the dependent variable = mean symptom score, and separately the QoL score (possibly after rank transformation). Potential predictor variables = VAS score during enteral lipid + placebo infusion, gastric emptying, age, gender, BMI
Relationship between sensation and plasma hormones during lipid infusion (Aim 2)	Using the VAS score from the enteral infusions and for hormones, the AUC values	Spearman correlations between the VAS score and the AUC values for the various hormones, overall and separately by group (FD,DM, controls)
Small intestinal tight junction proteins,	Protein expression, lactulose:mannitol	Assess the associations between permeability and protein expression, vs. the VAS score, based on Spearman

permeability, intestinal chemosensitivity	ratio, VAS score	correlations.
---	------------------	---------------

The sample size estimate is based on our previous study which evaluated intestinal chemosensitivity in functional dyspepsia in which the proportions with severe symptoms were assessed. [In the current proposal, symptoms during lipid infusion will be evaluated on a continuous VAS scale, likely providing the ability to detect smaller effect sizes]. The effect of lipid plus

Group	Proportions (%) with severe symptoms			

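### The overall hypothesis names GLP-1 in one place and CCK in another, and the Aim 2 correlation row does not say which hormone, group or arm decides Aim 2A

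*Combined protocol and SAP*

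**What the plan says.** The overall hypothesis appears twice in current text. In the Abstract it is that "intestinal chemosensitivity related to increased epithelial permeability and GLP-1 explains symptom severity in patients with functional dyspepsia", and the sentence goes on to include diabetes with dyspepsia. In Section 1 it is that "intestinal chemosensitivity related to increased epithelial permeability and CCK explains symptom severity in patients with DM with upper GI symptoms". The named mediator and the population both differ.

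Aim 2A (Section 1) predicts that chemosensitivity will be "associated with higher plasma CCK and GLP-1 concentrations". The evaluation sentence keeps to the same two hormones: "This hypothesis will be evaluated by comparing intestinal chemosensitivity (a) with plasma CCK and GLP-1 concentrations".

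The row of the Section 3.5 table labelled Aim 2 is wider. It specifies "Spearman correlations between the VAS score and the AUC values for the various hormones, overall and separately by group (FD,DM, controls"). It does not define which hormones are meant, and the lists elsewhere differ. Section 3.3(v) has six (insulin, C-peptide, GLP-1, CCK, ghrelin, PYY). The Abstract has seven, with GIP and glucagon added and ghrelin left out. The row also does not say whether subjects given exendin 9-39 are included, whereas the row above it restricts its VAS predictor to the lipid plus placebo infusion.

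**The concern.** A reader of the final report needs to know in advance what result would support Aim 2A. The plan leaves three things open: whether one hormone suffices or both are needed, whether the pooled or a within-group correlation counts, and which treatment arms enter. It states no error control across these choices.

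The mediator matters because the randomised drug is a GLP-1 receptor antagonist. Under the Abstract's hypothesis, the randomised comparison (Aim 2B) and the correlations (Aim 2A) bear on the same pathway. Under the Section 1 hypothesis, the randomised comparison does not test the named mediator.

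The pooled correlation has a separate weakness. The legend to Figure 1 in Section 2 reports that more patients with functional dyspepsia than controls had at least moderate symptoms during lipid infusion. If a hormone's AUC also differs between groups, pooling the groups gives a correlation even when there is none within any group. The same can happen across treatment arms if exendin shifts both the VAS score and a hormone.

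**Working it through.** The plan gives no count of correlations, error rate or power for this row, so there is no stated figure to reproduce.

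**Inputs from the document**
- Hormones: 2 in Aim 2A (Section 1); 6 in Section 3.3(v); 7 in the Abstract.
- Strata: 4, namely all subjects, functional dyspepsia, DM and controls (Section 3.5).
- Group sizes: 24, 40 and 40, total 104. With 1:1 randomisation the placebo arm has 12, 20 and 20, total 52.

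**Assumptions**
- Each correlation is tested at two-sided 0.05. Section 3.5 states this alpha for the sample size only.
- Inter-hormone correlation lies between 0 and 0.7. The document gives no value.

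**Number of tests**
- Aim 2A as worded: 2 × 4 = 8.
- Whole row: 6 × 4 = 24 (7 × 4 = 28 with the Abstract's list).
- Expected false positives with no true association: 8 × 0.05 = 0.4 and 24 × 0.05 = 1.2.

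**If the tests were independent**, P(at least one) = 1 − 0.95^k:
- k = 2 (both hormones, pooled sample only): 9.8%
- k = 8: 33.7%
- k = 24: 70.8%
- k = 28: 76.2%

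**Allowing for dependence.** The pooled test shares its subjects with the three group tests, and hormones may be correlated with each other. Null simulation of Spearman tests, 6000 trials, 24/40/40, with no group or arm differences:

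| Tests | r = 0 | r = 0.3 | r = 0.5 | r = 0.7 |
|---|---|---|---|---|
| 2 hormones, pooled only | 10.1% | 9.2% | 9.2% | 8.8% |
| 2 hormones × 4 strata | 30.3% | 29.0% | 28.4% | 27.4% |
| Same, positive direction only | 16.2% | 15.1% | 14.6% | 14.0% |
| 6 hormones × 4 strata | 66.5% | 62.9% | 56.6% | 48.9% |

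Here r is the assumed inter-hormone correlation. With the placebo arm only (12/20/20), the last three rows run from 30.7% to 26.9%, from 16.5% to 13.8%, and from 66.2% to 48.7%. The result therefore hardly depends on which arms are used.

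**Pooling.** The simulation has no group differences, so it does not include the pooling problem. The document gives no group means for the hormones, so that effect is not quantified here.

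**Error control over two hormones.** Testing each at 0.025 gives 1 − 0.975² = 4.9%.

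**Precision cost of the placebo arm alone.** The correlation detectable with 80% power is tanh[(z(1−α/2) + z(0.80)) × √(1.06/(n − 3))]. At α = 0.05:
- n = 104: tanh[(1.960 + 0.842) × √(1.06/101)] = 0.28
- n = 52: tanh[(1.960 + 0.842) × √(1.06/49)] = 0.39

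At α = 0.025 the values are 0.31 and 0.42.

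**The case against.** The strongest reply is that Aim 2A is already specific: it names two hormones and a direction, and says that it will be evaluated with those two. That stands. A reader of the Section 3.5 row might infer that Aim 2A is judged on about 24 correlations and would therefore look supported by chance in most trials. The document does not support this. A correlation with insulin, C-peptide, PYY or ghrelin cannot satisfy Aim 2A as written, and the figure of roughly one half to two thirds belongs to the whole row.

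A reader might also infer that the preliminary evidence contradicts itself, since Section 1 says "increased sensitivity was associated with higher plasma concentrations of CCK during lipid infusion" and Section 2 says "increased sensitivity was associated with higher plasma concentrations of GLP-1 during lipid infusion". It does not. The same paragraph of Section 1 goes on to report an association with GLP-1 during lipid infusion, so both associations may have been seen. Section 1 also gives CCK its own rationale: a CCK-A receptor antagonist blocked the sensitising effect of lipid.

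It is also fair to say that this is a mechanistic study, that the plan never calls these correlations confirmatory, and that nothing obliges Aim 2A to test only the pathway that exendin blocks. That limits the weight of the point. It does not settle which hypothesis is the study's own, or which of the eight correlations decides Aim 2A.

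**Conclusion.** The point holds in limited form. The Abstract and Section 1 give different mediators and different populations for the overall hypothesis and must be reconciled. The Aim 2 row is broader than Aim 2A and names no deciding hormone, stratum, treatment arm or adjustment.

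For Aim 2A's eight tests, the chance of at least one false positive is about 27 to 34%, where the upper end treats the tests as independent. It is about 14 to 17% if the association must be in the stated direction. For the 24-test row it is about 50 to 67%. These figures rest on an assumed two-sided 0.05 per correlation, inter-hormone correlations of 0 to 0.7, and no differences between groups. Such differences could raise the error of the pooled test further.

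**What to change.** 1. State one overall hypothesis, with the same mediator (or mediators) and the same population, in the Abstract and in Section 1.
2. For Aim 2A, prespecify one analysis for each of GLP-1 and CCK. Either stratify by, or adjust for, group and treatment arm, or limit the analysis to the lipid plus placebo arm as the second row of the table does. Stratifying by group alone is not enough, because half of each group receives the GLP-1 antagonist.
3. Control error over the two hormones. Use a fixed order, with GLP-1 first because exendin tests that pathway and then CCK, or use Holm.
4. Define the hormone list once. Label the other hormones and all by-group correlations exploratory, with false-discovery-rate-adjusted p-values.

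The change is to wording in the protocol and analysis plan; no subjects, samples or procedures are added. The cost is that the other correlations cannot be offered as tests of Aim 2A. Limiting the analysis to the placebo arm would also halve the sample from 104 to 52 and raise the detectable correlation from about 0.28 to 0.39 at two-sided 0.05. Adjusting for arm keeps all subjects, but includes some whose GLP-1 receptor is blocked.

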3.3 Details of Study Assessments

In patients with DM, fingerstick bedside reflectance meter blood glucose concentrations will be assessed during enteral infusion and gastric emptying studies at time 0, every 30 minutes for 2h, then at 120 and 180 minutes. For patients with type 1 and type 2 DM who are treated with insulin, insulin will be given according to the patient's sliding scale. For type 2 DM patients who are not on insulin, no insulin will be given.

i) Screening items include questionnaires (for overall functional GI symptoms [Rome III criteria], severity of dyspepsia [Nepean severity index], gastroparesis cardinal symptom index [GCSI], anxiety and depression [HAD], and autonomic symptoms), blood tests (CBC, glycosylated hemoglobin, fasting glucose, sodium, potassium, bicarbonate, calcium, chloride, phosphorous, AST, total bilirubin, alkaline phosphatase, creatinine, high sensitive C-reactive protein, tissue transglutaminase antibodies, and lipase), and EKG (to be reviewed by study physician). Some patients with diabetes mellitus have low serum lipase. Patients with serum lipase < lower limit of normal (i.e., < 10 IU/ml) will not be eligible to participate in the study.

Study procedures will be conducted over 3 days. Items (ii), (iii), (iv), and (v) below will be performed on the same day preferably before other study procedures. A tentative schedule is as follows: (ii) between 8 and 8.45 am, (iii) between 8.45 am and 11 am, (iv) can start while (iii) is in progress and (v) between 12.30 pm and 3 pm.

ii) Plasma pancreatic polypeptide (PP) response to sham feeding. Pancreatic polypeptide (PP) is secreted by the pancreas in response to hypoglycemia, ingestion of food or sham feeding secondary to vagal nerve stimulation. Vagal nerve injury blocks secretion. This assessment will be performed in the Charlton 7 CRU. Subjects will be fasting with NPO for 8 hours prior to this test. They must abstain from coffee or for 12 hours and stop all cholinergic agents for 48 hours before the test. During the sham feeding test, food is chewed and spit out (not swallowed) . After placement of an IV in the hand or forearm vein for blood draws, this hand will be placed in a hotbox heated to 55°C. Blood will be drawn in a lavender-top (EDTA) tube(s) at -5, 0, 5, 10, 15, 20, 25, and 30 minutes for PP. Spin down, keep specimen cold, and send 1.0 mL (0.5 mL minimum) of EDTA plasma frozen in plastic vial.

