v) Hormonal responses and symptoms during duodenal infusions. A small bore nasogastric tube will be inserted through the nostril into the stomach over a guidewire and advanced under fluoroscopic guidance until the infusion ports are in the 2nd part of the duodenum.

Thereafter, subjects in each group (ie, functional dyspepsia and DM) will be randomized to lipid infusion {66.7 mL Microlipid (0.5 gm/mL diluted in water to 222 ml)} together with placebo or exendin 9-39 in the ratio of 1:1. Lipids will be delivered into the duodenum at an infusion rate which matches the rate at which glucose enters the systemic circulation after oral glucose. After placement of an IV in the hand or forearm vein for blood draws, this hand will be placed in a hotbox heated to 55°C. We have considerable preliminary data for symptoms and hormonal responses with this paradigm. Plasma glucose, insulin, C-peptide, GLP-1, CCK, ghrelin, and PYY will be collected at 5 minute intervals for 30 minutes, 10 minute intervals from 30 – 60 minutes, and at 15 minute intervals from 60 – 180 minutes (18 times including 0 minutes).

vi) GLP-1 antagonist exendin 9-39 will be sourced from C.S. Bio, reconstituted in the Mayo Pharmacy by an established process used in previous studies, and undergo endotoxin testing, sterility testing and bacterial testing, and held in quarantine before it will be used in humans. Research compounded sterile preparations (CSP) are prepared and assessed for end preparation testing according to USP <797> in the hospital pharmacy services production lab. Each batch is tested for sterility according to USP <71> utilizing membrane filtration. The sterility testing is validated by a formulation Bacteriostasis Fungistasis test. The amount of each batch tested is determined by USP <71>. Each batch is tested for endotoxin according to USP <85>. High risk CSP are quarantined for 14 days and when all end preparation testing is completed.

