Plasma insulin concentrations will be measured using a chemiluminescence assay (Access Assay; Beckman Coulter, Chaska, MN). Established approaches will be used to estimate β cell responsiveness and insulin sensitivity from plasma glucose, insulin, and C-peptide concentrations.

Total ghrelin will be measured by a radioimmunoassay technique (Linco Research, Inc.). The assay uses 125I-labeled ghrelin and a ghrelin antiserum to determine the level of total ghrelin in plasma. There is no measurable crossreactivity to glucagon, GLP-1(7-36), insulin. (0.8 microL)

Summary of Blood Collections. The total blood collected for this study is 403 ml.

Item	Test ID	Lab	Tube (amount required)
Complete blood count [#]	9109	Central Clinical Lab	3 ml EDTA
Tissue transglutaminase antibody [#]	83671	Immunology Lab	5 ml red top (0.5 ml serum)*
High sensitive CRP [#]	82044	ICL	1 ml serum
Fasting glucose [#]	7702	ICL	2 ml Sodium fluoride (0.5 ml)
Lipase [#]	8328	Central Clinical Lab	5 ml SST (1 ml serum)
Glycosylated hemoglobin [#]	82080	Central Clinical Lab	3 ml EDTA (2 ml whole blood)
Sodium	81692	Central Clinical Lab	5 ml SST **
Potassium	81390	Central Clinical Lab	5 ml SST **
Bicarbonate	876	Central Clinical Lab	5 ml SST **
Calcium	8432	Central Clinical Lab	5 ml SST **
Chloride	8460	Central Clinical Lab	5 ml SST **
Phosphorus	8029	Central Clinical Lab	5 ml SST **
AST	8360	Central Clinical Lab	5 ml SST **
Total bilirubin	81785	Central Clinical Lab	5 ml SST **
Alkaline phosphatase	8340	Central Clinical Lab	5 ml SST **
Glucose ¹	7702	ICL	2 ml Sodium fluoride (0.5 ml)

GLP-1 ¹	80075	ICL	3 ml EDTA (1 ml plasma)
CCK ¹	90162	ICL	4 ml EDTA (2 ml plasma)
PYY ¹	7670	ICL	3 ml EDTA (1 ml plasma)
Total ghrelin ¹	83334	ICL	1.6 ml EDTA (0.8 ml plasma)
C-peptide ¹	7653	ICL	5 ml red top (0.5 ml serum)*
Insulin ¹	7661	ICL	5 ml red top (0.8 ml serum) *
Plasma PP ²		ICL	3 ml EDTA (1 ml plasma)
Epigenetic analysis (RRBS) ³	31669	BAP Lab	500 ng DNA (EDTA tube buffy coat - snap-frozen in liquid nitrogen)
DNA for SNPs ³	31669	BAP Lab	Use buffy coat from EDTA tubes
RNA analysis ⁴	31669	BAP Lab	3 PAX gene tubes (2.5 ml each, total = 7.5 ml)

* Same tube for these specimens; ** Same tube for these specimens; [#] Safety and screening assessments, one time only.

¹ Collected 18 timepoints during each study; ² Sham feeding test – 8 collections;

³ Requires DNA. Will be obtained from EDTA tubes for ghrelin and a separate 10 ml tube;

³ PAX gene tube

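### Aim 2C has no row in section 3.5, and its only stated evaluation is a with/without split on the PP response, with no PP summary, cut-off or handling of the exendin arm

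*Combined protocol and SAP*

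**What the plan says.** Section 1, Aim 2, hypothesises that chemosensitivity is "inversely associated with impaired abdominal vagal function". Part (c) of the evaluation is a comparison "in patients with and without and GI vagal dysfunction as assessed by the plasma pancreatic polypeptide response to sham feeding". It names no test, PP summary, threshold or covariate.

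Section 3.3 ii gives the sampling schedule: "Blood will be drawn in a lavender-top (EDTA) tube(s) at -5, 0, 5, 10, 15, 20, 25, and 30 minutes for PP". The blood-collection summary agrees ("Sham feeding test – 8 collections"). Neither place says whether the response is a peak, an area or a change from baseline, or what value counts as dysfunction. Section 2 (Vagal neuropathy) says the study will evaluate how well the sham-feeding response predicts sensorimotor dysfunction, but gives no method.

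Section 3.5 defines the outcome: "Chemosensitivity will be measured using a 100mmVAS anchored at each end". Its table has no row for PP or vagal function. The Aim 2 row covers Spearman correlations of VAS with hormone AUCs, and the regression row lists no PP term. Comparable measures (hormone AUCs, lactulose:mannitol ratio, protein expression) are kept continuous. The regression of daily symptoms on chemosensitivity (Aim 1B) takes VAS from the lipid plus placebo infusion only.

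Under section 3.3 v, patients receive the lipid infusion "together with placebo or exendin 9-39 in the ratio of 1:1", so half of each patient group has its VAS measured on exendin.

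**The concern.** Three things are left open for a named hypothesis.

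- **How PP is used.** Eight samples can be summarised in several ways, and any summary can be cut at many points. With neither fixed, both can be chosen once the results are visible.
- **The split itself.** If the relation is graded, two classes discard information that has already been collected. The loss grows as dysfunction becomes less common.
- **The exendin arm.** Aim 2B expects exendin to lower chemosensitivity. If Aim 2C used both arms with no arm term, that effect would sit in the residual variance. The vagal relation might also differ by arm, because section 1 describes enteral hormones as acting on receptors that are located on, or activate, vagal afferents.

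At stake is whether a null result for Aim 2C could be told apart from an insensitive analysis, and whether a positive one could be trusted.

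**Working it through.** **The plan's own figure.** No power is stated for Aim 2C. The roughly 80% in section 3.5 concerns exendin and group contrasts. For 10% vs 50% severe symptoms, 20 vs 20, two-sided 0.05, pooled variance: (0.40 − 1.96 × √(2 × 0.3 × 0.7/20)) / √((0.09 + 0.25)/20) = (0.40 − 0.284)/0.130 = 0.89, so power is 81%. The figure reproduces. It neither supports nor refutes this point, but it gives the planned exendin effect used below.

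**Inputs.** From the documents: 40 DM + 40 functional dyspepsia = 80 patients; 1:1 allocation, so about 40 on placebo; two-sided alpha 0.05. Assumed: a roughly normal PP summary, a linear relation to VAS, and 10% to 50% of patients classed abnormal. The documents give no PP distribution, prevalence of dysfunction or VAS SD.

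**Information kept by a split.** For a normal predictor cut so that a share p is abnormal, relative efficiency = φ(z_p)² / [p(1 − p)].

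| Share abnormal | φ(z) | Efficiency | Equivalent of 80 | Equivalent of 40 |
|---|---|---|---|---|
| 50% | 0.3989 | 0.637 | 50.9 | 25.5 |
| 30% | 0.3477 | 0.576 | 46.1 | 23.0 |
| 20% | 0.2800 | 0.490 | 39.2 | 19.6 |
| 10% | 0.1755 | 0.342 | 27.4 | 13.7 |

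**Effect on power, 80 patients.** By Fisher's z, a continuous PP summary with an arm term has 80% power at a within-arm correlation of tanh(2.80/√77) = 0.31. A split multiplies the correlation by the square root of the efficiency. At 50/50 this is 0.309 × 0.798 = 0.247, and power is Φ(atanh(0.247) × √77 − 1.96) = 60%. The same steps give 55% at 30/70, 49% at 20/80 and 36% at 10/90.

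**If the arms were pooled with no arm term.** The planned 10% vs 50% effect makes arm 0.2²/(0.3 × 0.7) = 19% of the variance of the binary outcome. On a latent normal scale d = 1.28, and the share is (d²/4)/(1 + d²/4) = 0.411/1.411 = 29%. Multiplying the correlation by √(1 − 0.29) takes the continuous analysis from 80% to about 65%. The split falls to about 46% (50/50), 42% (30/70) and 37% (20/80). The cost depends on the VAS effect, which is unknown: at d = 0.5 the share is 6%, the continuous analysis has 77%, and the split has 57%, 53% and 46%.

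**Can arm bias the comparison?** Sham feeding is scheduled "ii) between 8 and 8.45 am" and the infusion from 12.30 pm the same day. PP is thus measured before exendin or placebo, and arm is randomised within group. Vagal status can differ by arm only by chance.

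**The case against.** The strongest reply is that one sentence of aims prose is being read as a settled analysis. The sentence names no test, and the word impaired can describe a state, which a with/without contrast fits. This stands in part: the documented defect is that section 3.5 is silent on Aim 2C, and the split is simply the only evaluation stated anywhere.

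The information loss also depends on the assumed shape. Section 3.3 ii says vagal injury blocks PP secretion, which is compatible with a threshold. If VAS followed a step at the right cut-off, the same formula would describe the loss from a linear model, and a correct split would lose nothing. The documents do not settle this. It is a reason to keep the split as a secondary analysis, but it does not supply the missing cut-off.

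A reader might infer that the plan pools the exendin and placebo arms. It does not say so. The placebo-only VAS in the Aim 1B row makes a placebo-only reading equally open, in which case about 40 patients are available, not 80. A reader might also infer that exendin confounds the vagal comparison. Randomisation, with PP measured beforehand, rules out systematic confounding; what remains is lost precision and chance imbalance.

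Finally, the efficiency figures concern cutting one PP summary in two, not the eight samples as such. Any single-number summary also reduces the eight samples.

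**Conclusion.** The point holds in conditional form. Aim 2C is a named hypothesis whose only stated evaluation is a with/without comparison. PP summary, cut-off and handling of arm are all undefined, and section 3.5 has no row for it.

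Under a roughly normal PP summary and a linear relation, the split loses at least 36% of the information at the best possible cut and 66% if only 10% of patients are abnormal. Without those two assumptions the size of the loss is not known. Any cost from the exendin arm applies only if both arms are used without an arm term, and is then chiefly one of precision. The documents do not support the stronger readings that arms are definitely pooled, that exendin biases the comparison, or that a split must lose information whatever the shape.

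The change should be made but is not critical. Aim 2C is mechanistic, carries no power claim and affects no randomised comparison.

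**What to change.** Add one row to section 3.5 for Aim 2C:

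- **Main analysis:** regress infusion VAS (rank-transformed if clearly non-Gaussian, in line with the rank-based options elsewhere in section 3.5) on one pre-specified continuous PP summary, with terms for randomised arm and patient group. Incremental AUC over the mean of the −5 and 0 minute samples would serve. The essential step is to name a single summary.
- **Arm:** add a PP-by-arm term, or a placebo-arm-only sensitivity analysis consistent with the Aim 1B row, so that one common PP slope is not simply assumed.
- **Secondary:** keep the with/without dysfunction comparison, with its cut-off and source written down before the data are seen.

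The cost is one table row and one extra model, with no new samples or visits. The main analysis relies on an approximately monotone relation, which the secondary split helps to check. Restricting the main analysis to placebo patients would be simpler but dearer: at the correlation of 0.31 used above, 40 patients give Φ(0.319 × √37 − 1.96), or about 49% power, against 80% with both arms and an arm term.
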